3.5.2 Post-Testing Phase

The longer follow-up post-testing phase will provide exploratory information on whether the immediate post-testing improvement after 3 weeks of treatment can be sustained. The mean (95% CI) changes from baseline to immediate (within 1 week) post-testing, 4 weeks post-testing and 6 months post-testing will be reported. Box and whisker plots will be produced to show the distribution of naming accuracy over time by treatment group. To explore the longitudinal data, a general linear mixed model (GLMM) will be constructed by tDCS group for the dependent variable (anomia). The GLMM will incorporate random subject effects to account for repeated measurements being made on subjects; the model will include time, aphasia type, severity, and clinical center as independent variables. A similar modeling approach may be applied to other secondary outcomes.

3.6 Safety Analyses

All adverse experiences will be summarized in terms of frequency, severity and relatedness to the study treatment using the MedDRA code. All subjects who received tDCS will be included in the safety analysis. At the end of the study, the cumulative incidences of adverse events are compared between the two treatment groups using Fisher's exact test at the two-sided alpha level of 0.05.

The repeated measures of the FACES pain rating scale will be compared by treatment group by fitting a repeated measures proportional odds model.

3.7 DSMB Reporting

The study biostatistician will generate closed and open DSMB reports semi-annually or more frequently, as determined by the DSMB. Each DSMB report provides cumulative summary statistics on enrollment; subject status in the study (e.g., number completed study, drop outs, etc); baseline characteristics; safety data, including AEs and SAEs; and data quality information. The statistics for the closed DSMB Reports are provided by treatment group displayed as A or B. The open report contains aggregated statistics only, i.e., not by treatment group.

1. LIST OF ACRONYMS

- A- tDCS Anodal transcranial direct current stimulation
- ABA Apraxia Battery for Adults
- AE Adverse Event
- AQ Aphasia Quotient
- ASRS Apraxia of Speech Rating Scale
- BNT Boston Naming Test
- DCU Data Coordination Unit (at MUSC)
- DSMB Data Safety Monitoring Board
- ITT Intent-to-Treat
- PNT Philadelphia Naming Test
- PPTT Pyramids and Palm Trees Test
- S- tDCS Sham transcranial direct current stimulation
- SAE Serious Adverse Event
- SAP Statistical Analysis Plan
- SLP Speech Language Pathologist
- tDCS transcranial Direct Current Simulation
- trt Treatment Group
- tx Treatment
- WAB-R Western Aphasia Battery- Revised
- WAIS-III Wechsler Adult Intelligence Scale III Score
- WebDCU™ Web-based Clinical Trial Management System

2. STATISTICAL ANALYSIS PLAN AND STATISTICAL REPORTS

This document provides the details of the statistical analyses planned for the trial. Prior to locking the database and breaking the code, this Statistical Analysis Plan (SAP) will be updated. The SAP will define all “pre-specified, pre-planned analyses.”

The DCU Biostatistics Core under the direction of [name] will generate closed and open DSMB reports semi-annually or more frequently, as determined by the DSMB. Each DSMB report provides cumulative summary statistics on enrollment; subject status in the study (e.g., number completed study, drop outs, etc); baseline characteristics; safety data, including AEs and SAEs by MEDdra code, severity, and relatedness to the study intervention; and data management/quality information (e.g., timeliness and completeness of data entry by the clinical centers via the WebDCU™; number of data queries generated and resolved). The statistics for the closed DSMB Reports are provided by intervention group displayed as A or B. The open report contains aggregated statistics only, i.e., not by intervention group.

3. SYNOPSIS OF THE STUDY

A Randomized, Multi-Center, Double-Blind, Pilot Study of tDCS for stroke patients with aphasia

4. STUDY DESIGN AND OBJECTIVES

At total of 74 subjects from 2 sites will be randomized 1:1 to tDCS (n=37) or sham (n=37). This study design will allow us to assess whether it is futile to proceed with further study of tDCS in a larger Phase III trial.

The primary objective of the study is to compare tDCS versus sham-control in stroke patients with aphasia in order to assess whether it is futile to proceed with further study of tDCS.

Planned enrollment duration: approximately 4 years (0.77 patients /site/month)

Duration of follow-up in Primary Study Phase: 3 weeks

Duration of follow-up in Secondary Study Phase: 7 weeks from baseline

Duration of follow-up in Post-testing phase: 27 months from baseline

5. DEFINITION OF TARGET POPULATION

5.1 Target Population

Stroke patients with aphasia receiving a computerized treatment for anomia.

5.2 Intent-to-Treat Sample

The primary analysis will be analyzed under the intent-to-treat principle (ITT). Under this principle, the evaluable sample will include all participants who are randomized.

5.3 Safety Analysis Sample

All randomized participants who receive at least one session of the intervention are included in the safety analyses, regardless of the duration of intervention administered. Patients will be classified according to the treatment group that was actually received.

5.4 Per Protocol Sample

A secondary analysis of the primary outcome will be done, using the subset of patients defined by the Per Protocol Sample. This will be defined as having completed at least 80% of the expected study sessions on schedule. Patients will be classified according to the treatment group that was actually received. Patients for whom there were major protocol deviations will be excluded.

6. RANDOMIZATION AND BLINDING

The study is to be conducted in a double-blind manner. The subjects, the site investigators, and the USC and MUSC clinical staff involved in this study will not know the intervention assignment. Select members of the Data Coordination Unit (DCU) will be partially blinded, i.e., they will know the intervention group assignment as A or B, but not whether the patient receives active tDCS or sham. The study statistician and the DSMB will have a sealed envelope with the intervention group identifiers. This envelope would only be opened if the study statistician is directed to open it by the DSMB or at the end of the futility study.

The randomization will take place centrally via the trial Website (WebDCU). Subjects will be randomized 1:1 (A-tDCS: S-tDCS). The objective of subject randomization is to protect the randomness of treatment allocation and to prevent serious imbalances in site, baseline age, aphasia type, and severity (as measured by the WAB-R). The block urn method (Zhao et al. 2011) and the minimal sufficient balancing method (Zhao et al. 2012) will be used. The computer program developed at the DCU makes the treatment assignment based on the current status of treatment group distribution within each stratum as well as overall balance of treatment assignment. The randomization scheme will never be deterministic.

A “Real-Time” randomization procedure is implemented via the Trial Website on the WebDCU™ System where the clinical center staff enters the basic baseline (e.g., age, aphasia type, and AQ severity) and eligibility information of a subject prior to enrollment. If the subject’s eligibility status is confirmed, the computer program on the WebDCU™ server will evaluate the treatment arm distribution and generate a treatment assignment based on the randomization scheme. The clinician (speech-language pathologist – SLP) enrolling the patient will not see the treatment assignment, only a numeric patient number.

7. BASELINE INTERVENTION GROUP COMPARABILITY

During the course of the study as a part of the DSMB reports, summary statistics for the following baseline variables will be computed and compared between intervention groups. At study conclusion, the statistical tests for comparison will be two-sample *t*-test or Wilcoxon rank sum test for continuous scale variables and chi-square or exact test for categorical variables.

Demographic:

- Mean age
- Gender
- Mean years of education

Clinical characteristics:

- WAB-R summary scores
- BNT Score Summary
- ABA
- PPTT
- PNT
- Cinderella Story
- ASRS
- WAIS-III

8. PRIMARY ANALYSIS

8.1 Primary Outcome

The primary outcome will be the change in the number of correctly names items on the PNT (plus a portion [N=80] of the trained items) (where change from pre-treatment to immediate post-testing). To assess change in naming ability, the primary outcome in this study will be administered twice (and averaged to reduce variability) on two consecutive days immediately before treatment starts and twice after treatment is completed. The change will be computed as the difference in the number of correctly named items between the average of the two pre-treatment assessments to the average of the two post-treatment sessions. The PNT is a computer based assessment of naming in persons with aphasia and includes 175 pictures representing mid- and high-frequency nouns from a word frequency list compiled by Francis and Kucera (1982).

8.2 Statistical Hypotheses

The primary hypothesis is:

$$H_0: \mu_T - \mu_S \geq \delta$$

vs

$$H_A: \mu_T - \mu_S < \delta$$

where μ_T is the expected change (pre-treatment and immediate post-testing) in the number of correctly named items for the treatment arm, μ_S is the expected change in the sham control group, and δ is the minimum improvement sufficient to warrant further evaluation of tDCS treatment. We define that minimum improvement to be 1.5 points more than the observed change in the sham control group. If we reject the null hypothesis, then tDCS is considered clearly ineffective (in improving anomia in stroke patients) and will not be considered for further study. If we fail to reject the null hypothesis, we would consider undertaking a Phase III study of tDCS.

8.3 Sample Size Determination

In preliminary studies, the mean difference in change from baseline in the active and sham groups in naming accuracy was ~2.5 points (Baker, Rorden, & Fridriksson, 2010, Fridriksson et al., submitted). In one study, the S-tDCS (sham) group improved ~1.2 point from baseline to 1 week (Baker, Rorden, &

Fridriksson, 2010). In another study, the S-tDCS group improved ~3.9 points from baseline to 1 week (Fridriksson et al., submitted). For power calculations, we assumed the mean change from baseline to immediate (1 week) post-testing for the A-tDCS group under the null hypothesis of non-futility is equal to $\mu_s + \delta = 4 + 1.5 = 5.5$. When the sample size is 33 per group, a two sample t-test with a 0.10 one-sided significance level will have 85% power to reject the null hypothesis that the A-tDCS treatment is 1.5 points better than S-tDCS (sham) and declare futility when the A-tDCS treatment comes from a distribution with mean change of 4 (assuming the pooled SD is 2.6). As with most clinical studies, a certain amount of drop-outs (including subject withdrawal or lost-to-follow-up) can be expected. In preliminary studies less than 5% of visits were missing. Conservatively assuming the drop-out rate to be no more than 5% over 5 weeks, the required sample size was inflated from 33 to 37 per intervention arm to account for the effect of the drop-outs in the intent-to-treat analysis using an inflation factor (Friedman, et al, 1985).

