2. STUDY PROCEDURES

2.1 Study Procedures Overview

After informed consent is received, a neurological examination will be performed and multiple screening assessments will be conducted including a tDCS and MRI safety screening (see below). If the patient passes the initial screening portion, speech and language diagnostic testing will be conducted during the same visit (Visit 1). During the next two visits (Visits 2 and 3), patients will undergo baseline assessments of naming ability and connected speech, and structural and functional MRI examinations. The fourth visit will include collection of blood sample, electrode positioning and tDCS treatment administration. Patients will receive 15 sessions (Visits 4-18) of tDCS treatment administration. At the beginning of Visit 4, eligible patients will be randomized to receive either A-tDCS (1 mA) or S-tDCS (placebo) for 15 consecutive weekdays (20-min per each 45-min behavioral treatment session). A computerized anomia treatment will be coupled with the stimulation. The computerized treatment task will be 45-minutes in total length, so that it will commence at the same time as the tDCS administration and continue for another 25-minutes after the tDCS has ceased. To assess cardiovascular arousal, blood pressure and heart rate will be measured before and after each session. Additionally, discomfort ratings will be recorded following the end of each session using the *Wong-Baker FACES Pain Rating Scale* and a weekly neurological exam will be administered by a neurologist. Utilizing a computerized picture naming assessment (which combines the 175 items from the PNT and 80 treated items) of trained and untrained nouns, all patients will be assessed at 8 different time points throughout the experiment: twice at baseline (Visit 2 and 3), twice immediately following the fifteenth (and final) treatment session (Visit 19 and Visit 20), twice at 4 weeks follow-up (Visit 21 and Visit 22), and twice at 6 months follow-up (Visit 23 and Visit 24).

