3.4 Primary Analysis

3.4.1 Primary Outcome

The primary outcome will be defined as the change in number of correctly named items on the PNT (pre-treatment and immediate post-testing). To assess change in naming ability, the primary outcome in this study, the PNT (plus a portion [N=80] of the trained items) will be administered twice (and averaged to reduce variability) on two consecutive days immediately before treatment starts and twice after treatment is completed. The change will be computed as the difference in the number of correctly named items comparing the average of the two pre-treatment PNT assessments to the average of the two post-treatment PNT sessions.

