3.4.3 Sample Size Determination

In preliminary studies, the mean difference in change from baseline in the active and sham groups in naming accuracy was ~2.5 points (Baker, Rorden, & Fridriksson, 2010, Fridriksson et al., 2011). In one study, the S-tDCS (sham) group improved ~1.2 point from baseline to 1 week (Baker, Rorden, & Fridriksson, 2010). In another study, the S-tDCS group improved ~3.9 points from baseline to 1 week (Fridriksson et al., 2011). For power calculations, we assumed the mean change from baseline to immediate (1 week) post-testing for the A-tDCS group under the

null hypothesis of non-futility is equal to $m_s+d=4+1.5=5.5$. When the sample size is 33 per group, a two sample t-test with a 0.10 one-sided significance level will have 85% power to reject the null hypothesis that the A-tDCS treatment is 1.5 points better than S-tDCS (sham) and declare futility when the A-tDCS treatment comes from a distribution with mean change of 4 (assuming the pooled SD is 2.6). As with most clinical studies, a certain amount of drop-outs (including subject withdrawal or lost-to-follow-up) can be expected. In preliminary studies less than 5% of visits were missing. Conservatively assuming the drop-out rate to be no more than 5% over 5 weeks, the required sample size was inflated from 33 to 37 per treatment arm to account for the effect of the drop-outs in the intent-to-treat analysis using an inflation factor (Friedman, et al, 1985).

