9.4 Exploratory Analyses of BDNF polymorphism

A two group *t*-test with a 0.05 two-sided significance level will have 80% power to detect a difference in mean reaction time of 2.6, assuming that the common standard deviation is 2.6, when the sample sizes in the two allele groups are 12 having at least 1 MET allele and 25 without the MET allele, respectively (a total sample size of 37 patients in the A-tDCS group assuming 33% have at least 1 MET allele).

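### Does the SD of 2.6 behind the sample size really belong to naming change, given that SAP 9.4 attaches the same figure to reaction time?

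*SAP*

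**What the plan says.** **Primary sizing.** SAP 8.3 and Protocol 3.4.3 carry the same calculation: one-sided 0.10 test, margin 1.5 points, true difference zero, and 33 per arm for 85% power. SAP 8.3 sets that power to "declare futility when the A-tDCS treatment comes from a distribution with mean change of 4 (assuming the pooled SD is 2.6"), and the Protocol likewise has "assuming the pooled SD is 2.6". The hypotheses in SAP 8.2 make the quantity the pre-to-post gain in items named correctly. SAP 8.4 restates the complement of the power as a 15% chance of wrongly going on to Phase III.

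**BDNF comparison.** SAP 9.4, headed exploratory, compares MET carriers with non-carriers among the 37 active-arm patients. It claims 80% power for a "difference in mean reaction time of 2.6, assuming that the common standard deviation is 2.6". It names no other dependent variable.

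**Reaction time elsewhere.** It appears nowhere else in either document. It is not among the outcomes in Protocol 3.4.1 and 3.5.1 or SAP 8.1 and 9.1, and it has no unit or visit. The treatment task (Protocol 2.2.8) saves a response file and shows an accuracy score. The naming assessment (Protocol 2.2.4) sets a 20-second limit per trial.

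**Timing of SAP changes.** SAP section 2 commits to updating the SAP before database lock and before the code is broken.

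**The concern.** A count of pictures and a response time have no reason to share an SD, and neither section gives a source for 2.6. The citations in 8.3 support the mean changes and are not tied explicitly to the SD. One label therefore looks wrong.

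If the wrong label is in 9.4, the only sentence describing the BDNF analysis names a variable the trial does not define, and the analyst would have to choose one later. If instead 2.6 were a reaction-time SD carried into 8.3, then the 33 per arm, the 85% power and the 15% false-go rate would not rest on the primary outcome. A trial that failed to declare futility would then tell the sponsor less than 8.4 promises.

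Two neighbouring points seem to add doubt about what 2.6 measures:

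- **Interval.** In a preliminary study "the S-tDCS (sham) group improved ~1.2 point from baseline to 1 week", whereas this trial gives A-tDCS or "S-tDCS (placebo) for 15 consecutive weekdays".
- **Item set.** Protocol 3.4.1 first says "The primary outcome will be defined as the change in number of correctly named items on the PNT" and then "the primary outcome in this study, the PNT (plus a portion [N=80] of the trained items) will be administered twice", while SAP 8.1 scores "correctly names items on the PNT (plus a portion [N=80] of the trained items").

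**Working it through.** **1. Primary sample size** (inputs from SAP 8.3: one-sided alpha 0.10, power 0.85, margin 1.5, true difference 0, SD 2.6).

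- n per arm = 2 × (z0.90 + z0.85)² × (SD/margin)² = 2 × (1.2816 + 1.0364)² × (2.6/1.5)² = 2 × 5.373 × 3.004 = 32.3, rounded up to 33.
- Power at 33 per arm: standard error 2.6 × √(2/33) = 0.640; noncentrality 1.5/0.640 = 2.34 on 64 df; power 85.2% by noncentral t (85.6% by normal approximation).
- False-go rate = 100 − 85.2 = 14.8%, against the stated 15%.
- Inflation: 33/0.95² = 36.6, rounded up to 37, as stated. With 35 evaluable (37 × 0.95 = 35.15) power is 86.8%; with 37 it is 88.2%. False-go is then about 13% and 12%.

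**2. BDNF power** (inputs from SAP 9.4: two-sided 0.05, groups of 12 and 25, difference 2.6, SD 2.6).

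- 37 × 0.33 = 12.2, so 12 carriers and 25 non-carriers.
- Noncentrality = (2.6/2.6)/√(1/12 + 1/25) = 1/0.351 = 2.85 on 35 df; power 79.1% by noncentral t, 81.3% by normal approximation. The stated 80% lies between.
- The value 2.6 cancels. The statement says only that a one-SD difference is detectable with about 80% power, and that is true in points, seconds or any other unit.

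**3. The two sections side by side.** In SAP 8.3 the SD shares a sentence with a mean change of 4 and a margin of 1.5 points. The sentences before it give a preliminary active-minus-sham difference of about 2.5 points in naming accuracy and sham gains of about 1.2 and 3.9 points. SAP 8.2 defines the quantity as items named. Protocol 3.4.3 repeats all of this in a document with no reaction-time variable. In SAP 9.4 the only trace of reaction time is the label itself.

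**4. What each possible explanation would change.**

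- *The 9.4 label is wrong and naming change was meant:* nothing in 8.3 or 8.4 changes, and the 9.4 power stands.
- *Reaction time was meant, and 2.6 was borrowed from 8.3 or is a coincidence:* 8.3 and 8.4 are again untouched, and the 9.4 power still holds for a one-SD difference.
- *2.6 is a reaction-time SD used by mistake in 8.3:* only this would affect the primary sizing, and no statement in either document points to it.

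**5. Effect on the decision.** The futility test uses the SD observed in the data, so its 10% type I error does not depend on 2.6 under any of the three explanations.

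**The case for a change.** The strongest case is that the third explanation cannot be excluded from the text and that the design has little slack. False-go stays at or below 15% only up to an SD of 2.61 with 33 evaluable per arm, 2.69 with 35 and 2.77 with 37. At an assumed SD of 3.0 it would be 23% with 33 per arm. Reaction time is also not absurd in this trial: sessions are video-recorded and the treatment task saves responses, so a latency might be extracted.

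Part of this stands. The variable in 9.4 is undefined, and 8.3 does not say where 2.6 comes from.

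The step to a sizing fault does not stand. An SD of 3.0 is an assumption with no basis in the documents, and an unknown SD could as well be smaller: at 2.0 the false-go rate with 33 per arm is 4%. Sensitivity to the SD is a feature of any trial of a mean. A missing citation is a reporting gap and does not show that the figure belongs to another measure.

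The supporting points are weak as well. SAP 8.3 itself calls the immediate post-test the 1-week one, and Protocol 3.5.2 and SAP 9.3 place it within a week, so 1 week may mark the assessment point and not the length of treatment. Whether the 80 trained items count is a separate question about the outcome definition and says nothing about reaction time.

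As for the freedom to choose a variable in 9.4, that comparison is exploratory, confined to at most 37 patients, and feeds no decision. The SAP is due to be updated before the code is broken.

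**Conclusion.** This is a clerical slip in one exploratory power statement, most likely a wrong label. Its effect on the primary design is nil: 33 per arm, 85% power (85.2% recomputed), 37 after inflation and the 15% false-go rate all follow from the stated inputs, and those inputs are consistently expressed in naming points. The 9.4 power (79.1% against a stated 80%) does not depend on which variable was meant.

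The conclusion assumes that 2.6 in 8.3 is what its context says, the SD of the gain in items named. The documents give no reason to think otherwise, although they do not cite its source. Naming the variable in 9.4, and if convenient the origin of 2.6, is ordinary tidying for the SAP update already promised. It changes no number, test or decision rule, so no change to the plan is called for.

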8.4 Multiplicity

Since this is a phase II study, the false positive error rate has been relaxed (Schoenfeld 1980). For a futility design the type I and type II error rates are reversed as compared to a traditional, superiority hypothesis. For the primary analysis, the probability of incorrectly declaring a drug futile is 0.1 (or 10%, type I error is the false negative rate). Given that the active tDCS comes from a distribution with a mean change of the control group (e.g. the treatment is like the sham change), the probability of incorrectly moving to a Phase III trial is 0.15 (or 15%, type II error is the false positive rate).

For secondary outcomes and safety analyses, no adjustment of Type I error probability will be considered, since they will be treated as exploratory.

